## 7. Ethical Considerations

This study applies for a **waiver of informed consent** because:

- Data originate from routine clinical care
- The study poses no more than minimal risk
- Waiver will not adversely affect participant rights
- The study cannot be practicably conducted without the waiver
- Privacy and confidentiality will be strictly protected

The protocol and waiver request will be reviewed and approved by the institutional ethics committee.

## 8. Data Management

- Data will be stored in a secure, password-protected database (Access).
- Double data entry will be performed.
- Source data verification will occur before database lock.
- After locking, no changes will be made; corrections may be applied during statistical programming if necessary.
- Participants will be identified only by study ID codes.

## 9. Statistical Analysis Plan (SAP)

### 9.1 Sample Size

All eligible patients from 2016–2023 will be included. Estimated sample size: **~3,000 patients**.

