## 1. Background and Rationale

*Helicobacter pylori* (H. pylori) infection is highly prevalent in China and is associated with chronic gastritis, peptic ulcer disease, gastric mucosa-associated lymphoid tissue lymphoma, and gastric cancer. Increasing antibiotic resistance has reduced eradication success rates in real-world clinical practice.

Shenzhen Hospital of Southern Medical University manages more than 5,000 H. pylori tests and over 2,000 eradication treatments annually. Despite standardized training, eradication success rates remain suboptimal (<80% in internal data).

This study aims to evaluate the real-world effectiveness of commonly used eradication regimens and identify factors associated with treatment outcomes.

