## 3. Study Design

This is a **single-center, retrospective, observational study** using routinely collected clinical data from Shenzhen Hospital of Southern Medical University.

- **Study Period:** 2016–2023
- **Study Type:** Observational
- **Time Perspective:** Retrospective
- **Sampling Method:** Non-probability, consecutive sampling
- **Intervention:** None (standard-of-care only)

No study-driven treatment or randomization will occur. All treatments are determined by treating physicians as part of routine care.

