## 5. Data Sources and Data Collection

Data will be extracted from electronic medical records (EMR), including:

1. Demographics (age, sex)
2. *H. pylori* testing method and results (C13 breath test, histology, culture, external hospital data)
3. DOB values for C13 testing
4. Comorbidities
5. Allergy history
6. Concomitant medications
7. Number of eradication attempts
8. Treatment regimen details (drug names, doses, duration, regimen abbreviation)
9. Post-treatment test results

No additional visits, tests, or procedures will be performed.

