## 6. Outcome Measures

### 6.1 Primary Outcome

***H. pylori* eradication success rate**, defined as a negative post-treatment test (C13 breath test, stool antigen, histology, or other accepted method) within 4–12 weeks after therapy.

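### Is an estimate of about 3,000 patients at odds with more than 2,000 treatments a year, and could incomplete capture go unnoticed?

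*Combined protocol and SAP*

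**What the plan says.** Section 9.1 sets the inclusion rule, "All eligible patients from 2016–2023 will be included", and then estimates about "3,000 patients". It gives no source for the estimate, no precision target and no power calculation. Section 3 describes the sampling as "Non-probability, consecutive sampling". Section 1 says that the hospital "manages more than 5,000 H. pylori tests and over 2,000 eradication treatments annually" and does not say to which year or years this applies.

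Eligibility in sections 4.2 and 4.3 is broad: age 14 or over, tested and/or treated, and diagnosed as infected. The exclusions are pregnancy, breastfeeding and unsuitability in the investigator's judgement. A follow-up test is not an eligibility criterion. The test "within 4–12 weeks after therapy" appears only in the outcome definition (section 6.1).

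On data checks, section 8 plans double entry and states "Source data verification will occur before database lock". It adds "After locking, no changes will be made", but the same sentence lets errors be corrected in the analysis programs where needed. Section 10 has quality control staff check accuracy and adherence to the protocol.

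**The concern.** A study of all eligible patients should yield roughly what the hospital's volume implies, and the two figures look far apart. The estimate equals one and a half years of the stated treatment volume, for a period of eight years. Nothing in sections 4.2 and 4.3 obviously reduces the larger number to the smaller.

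Two explanations would matter. Extraction might be expected to miss many courses, or the figure might silently mean patients who came back for a follow-up test. In either case the captured patients could differ in success from the rest. The eradication rate and the regimen comparison would then be shifted, and a larger sample would not correct it. Double entry and source verification work on records already extracted, so they cannot find a course that never entered the database. The adherence check in section 10 names no count to compare against.

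**Working it through.** **Inputs.** About 3,000 patients (section 9.1); over 2,000 treatments a year and success below 80% (section 1); 2016–2023, taken as 8 full calendar years (section 3). Growth in volume and courses per patient are not in the documents and are assumed below.

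**1. Can 3,000 be reproduced?** No. The plan gives no inputs for a formula. Chosen inputs come close: a half-width of 1.43 points at an 80% rate needs 1.96² × 0.16 / 0.0143² ≈ 3,006, and 75% against 80% with 90% power needs 2,928 in total. The plan states none of these as design inputs, so neither is a reproduction.

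**2. Implied volume.** Courses per patient = total courses / 3,000.

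| Volume 2016–2023 | Total courses | Courses per patient |
|---|---|---|
| Constant 2,000 a year (assumed) | 8 × 2,000 = 16,000 | 5.33 |
| Linear rise 250, 500, …, 2,000 (assumed) | 250 × 36 = 9,000 | 3.0 |
| Geometric rise 100 to 2,000, ratio 20^(1/7) = 1.534 (assumed) | 5,557 | 1.85 |

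Under constant volume, 3,000 / 16,000 = 18.75%.

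**3. Courses per patient to expect.** If each course succeeds with probability p and every failure is re-treated at this hospital until success, the mean is 1/p: 1.25 at 80% and 1.43 at 70%. A mean of 1.85 would imply p = 1/1.85 = 54%. Under these assumptions, a geometric rise fits 3,000 treated patients only if 2016 held about 10 to 26 courses. So the tension is real, but its size depends on early volumes that the documents do not give.

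**4. What would incomplete capture do?** The half-width is 1.96 × √(p(1 − p)/3,000): 1.43 points at 80% and 1.64 at 70%, if all 3,000 have an outcome. The shift in the rate is (1 − coverage) × (captured rate − missed rate). At an 80% rate it exceeds the half-width when the two rates differ by more than 1.43 / (1 − coverage):

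- 95% coverage: 28.6 points
- 90%: 14.3 points
- 75%: 5.7 points
- 50%: 2.9 points

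Coverage is unknown, so these are thresholds and not estimates of bias. They are also for the pooled rate. For an assumed regimen with 300 outcomes the half-width is 1.96 × √(0.16/300) = 4.5 points, and the 95% threshold becomes 90.5 points, which is impossible from 80%. The figures therefore do not support a fixed coverage trigger by year or regimen.

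**5. Where is 3,000 used?** Sections 9.1 and 9.2 were searched for a rule that depends on it. There is none: no extraction target, no stopping point and no test sized to it.

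**The case for a change.** The strongest case for a change is that about 3,000 is the only expected yield in the plan, so an extraction that reached it might be accepted as complete. One count of eradication prescriptions by year and regimen would settle the matter cheaply. It is best done before lock, because correcting values in the analysis programs does not reveal a course that was never extracted.

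Part of this stands. No section names a completeness count, and double entry and source verification cannot replace one. The estimate has no stated source, and it is unclear whether it counts eligible, treated or tested patients.

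The rest is weaker. Nothing in the plan makes 3,000 a benchmark, so the idea that reaching it would look complete is conjecture. The inclusion of all eligible patients is itself a protocol requirement, so the adherence check in section 10 covers it in principle, though it is unspecified. A raw prescription count would also mislead: it includes patients under 14, pregnant or breastfeeding women and others properly excluded under section 4.3, and it counts courses where the plan counts patients. If the same query of the medical records supplied both the extraction and the count, a course that it missed would be absent from both.

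**Conclusion.** The concern identifies missing detail, not an error. The gap between 3,000 patients and about 16,000 courses appears only if today's volume is assumed for every year since 2016. Under other assumed growth the requirement falls from 5.3 to 1.85 courses per patient, and the documents cannot decide between them. A retrospective study of all eligible patients needs no power calculation, and at 3,000 outcomes the pooled rate is already precise to about 1.4 to 1.6 points.

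The rule that governs the result is inclusion of all eligible patients. If it is followed, the study population is right whether 3,000 proves too low or too high. The usual patient-flow account, giving the numbers eligible, excluded by reason, treated and tested in the outcome window, would show any shortfall and what the 3,000 refers to. Analysts supply this in reporting without an amendment.

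This conclusion rests on two assumptions: that the site applies the inclusion rule as written, and that treatments can be identified in the medical records, as section 5 implies. How treated patients without a follow-up test enter the primary denominator is a separate question, which this conclusion does not settle.

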### 9.2 Statistical Methods

#### Descriptive Analysis

- Continuous variables: Mean  $\pm$  SD
- Categorical variables: counts and percentages

#### Univariate Analysis

- t-test for continuous variables
- Chi-square test for categorical variables

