## 2. Study Objectives

### 2.1 Primary Objective

To determine the real-world eradication success rate of different H. pylori eradication regimens.

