### 2.2 Secondary Objectives

- To identify demographic, clinical, and treatment-related factors associated with eradication success or failure.

- To compare the effectiveness of commonly used eradication regimens in routine clinical practice.

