### 4.2 Inclusion Criteria

- Age  $\geq$  14 years
- Underwent *H. pylori* testing and/or eradication treatment during the study period
- Diagnosis of *H. pylori* infection based on national consensus guidelines or clinically accepted methods

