### 4.3 Exclusion Criteria

- Age  $<$  14 years
- Pregnant or breastfeeding women
- Patients deemed unsuitable by the investigator

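### No index course or unit of analysis is named, and regimens are not compared within treatment line, so crude percentages and a chi-square test would mix first-line and rescue courses

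*Combined protocol and SAP*

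**What the plan says.** Section 2.1 aims to estimate the "real-world eradication success rate of different H. pylori eradication regimens". Section 2.2 adds a second aim, "To compare the effectiveness of commonly used eradication regimens in routine clinical practice", and section 6.2 lists the comparison of rates between regimens as a secondary outcome. Section 3 leaves the choice of treatment to the treating doctor.

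Section 4.2 admits infected patients aged 14 or over who had "testing and/or eradication treatment during the study period". Section 4.3 excludes on age, on pregnancy or breastfeeding, and "Patients deemed unsuitable by the investigator"; earlier eradication therapy is not on the list. Section 9.1 takes everyone eligible, about 3,000 patients.

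Repeat courses are expected. Section 5 extracts "Number of eradication attempts", and section 6.2 has an outcome for how many attempts were needed. Section 5 also names "external hospital data" as a source for test results, but does not say whether the attempt count includes courses given elsewhere or before 2016.

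Section 6.1 defines success by a negative test "within 4–12 weeks after therapy", without saying which course of therapy. Section 9.2 then gives counts and percentages, a t-test, "Chi-square test for categorical variables", and a multivariable logistic regression with no covariate list. No section defines an index course, says whether the row is a patient or a course, or restricts or stratifies any analysis by treatment line.

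**The concern.** Two gaps act together.

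- **Confounding by line.** When doctors choose the regimen, the choice can depend on whether earlier treatment failed. If rescue courses succeed less often, a regimen used more often for rescue looks worse than an equally good one used mostly first-line. The distortion can also run the other way and hide a real advantage.
- **Undefined row.** With no index course or unit of analysis, two analysts could follow the plan faithfully and produce different rates. One might use first courses and the other all courses. If all courses are pooled, some patients contribute several rows, and neither the ordinary chi-square test nor ordinary logistic regression allows for that.

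At stake are the comparative aim in section 2.2 and the meaning of the rates reported by regimen under section 2.1.

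**Working it through.** **What the documents supply.** About 3,000 patients (section 9.1), two-sided tests at 0.05 (section 9.2), and overall success below 80% in internal data, not split by line (section 1). The 3,000 is a headcount with no power or precision target behind it, so there is no figure to reproduce. Line mix, success by line and number of regimens are not given. Every input below is therefore an assumption.

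**Crude gap with no true difference.** Success is 80% first-line and 65% rescue for both regimens. Regimen A is used first-line in 95% of courses, B in 70%.

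- A: 0.95 × 0.80 + 0.05 × 0.65 = 0.7925
- B: 0.70 × 0.80 + 0.30 × 0.65 = 0.7550
- Crude gap: 3.75 points; true gap within line: 0

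Rejection by the crude chi-square test (normal approximation) is 19.5%, 29.4% and 51.8% at 300, 500 and 1,000 per regimen. Simulation with 20,000 runs gives 19.9%, 29.4% and 52.1%. On the same data, a first-line-only test rejects 4.9% to 5.0% of the time, and a Cochran-Mantel-Haenszel test by line 4.9% to 5.1%. Logistic regression with line as a covariate (1,000 runs each) rejects 5.7% at 500 and 3.6% at 1,000. Simulation error there is about √(0.05 × 0.95/1,000) = 0.7 points.

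**Range over other assumptions.**

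- First-line use 95% vs 85%: 0.7925 vs 0.7775, gap 1.5 points, rejection 8.9% / 12.9% at 500 / 1,000.
- Rescue success 75%, mix 95% vs 70%: 0.7975 vs 0.7850, gap 1.25 points, rejection 7.7% / 10.6%.
- First-line success 85%, mix 90% vs 70%: with rescue 75%, 0.84 vs 0.82, gap 2.0 points, rejection 13% at 500. With rescue 60%, 0.825 vs 0.775, gap 5.0 points, rejection 50% at 500.
- Equal mix, or equal success by line: no gap, rejection 5%.

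**Masking.** Keep A as in the main case and make B truly 5 points better at each line (85% and 70%). B's crude rate is 0.70 × 0.85 + 0.30 × 0.70 = 0.8050, so the crude gap is only 1.25 points. Simulated power at 500 / 1,000 is 8.0% / 10.6% for the crude test and 48.4% / 77.5% for Cochran-Mantel-Haenszel.

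**Choice of row.** Assume success of 80%, 65% and 50% at attempts 1, 2 and 3, with 70% of failures retreated. Per patient starting treatment:

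- Second courses: 0.20 × 0.70 = 0.14
- Third courses: 0.14 × 0.35 × 0.70 = 0.0343
- Successes: 0.80 + 0.14 × 0.65 + 0.0343 × 0.50 = 0.9082
- First-course rate: 80.0%
- All-course rate: 0.9082 / 1.1743 = 77.3%

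The two rates differ by 2.7 points. With 50% to 90% of failures retreated, the all-course rate is 78.2% to 76.4%.

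**The case against.** The strongest reply is that the plan already contains the remedy. Univariate tests are unadjusted by design, and section 9.2 follows them with a multivariable model. Section 2.2 asks that model to cover treatment-related factors, and section 5 collects the attempt count, so it is an obvious candidate covariate. With line in the model, the simulations above return close to 5%. This stands: if attempt number enters the model, the confounding by line is largely removed. But the plan does not say that it enters, the outcome row is still undefined, and the percentages and chi-square result would be reported unadjusted beside the model.

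Three stronger readings are tempting, and the documents do not support them.

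- **That the chi-square test is the designated regimen comparison.** Section 9.2 assigns it only to categorical variables. Apart from the regression it is the only named test suited to comparing proportions, so its use is likely, but it is not stated.
- **That reported success could range up to each patient's last course.** Under the same retreatment assumptions that would be 90.8%. No section suggests this reading. Section 6.1 times the test from therapy, which reads most naturally as course by course, and section 6.2 treats attempts needed as a separate outcome.
- **That the all-lines rate is itself wrong.** As a description of routine practice it serves section 2.1 well. Only its use to rank regimens is at fault.

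It is also fair to say that other possible confounders go unnamed and that every magnitude here is assumed.

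**Conclusion.** The point holds in conditional form and should be fixed before analysis. It is certain that the plan admits all treatment lines, anticipates repeat courses, names neither an index course nor a unit of analysis, and has no within-line regimen comparison. It is not known how much this matters in these data. The crude comparison is biased only if line mix differs between regimens and success differs by line. In the scenarios tried with no true difference, the crude gap runs from zero to 5 points. The main illustration gives 3.75 points and rejection of about 29% / 52% at 500 / 1,000 per regimen; its milder variants give 1.25 to 1.5 points and 8% to 13%. These figures show how the bias works and do not estimate its size in this study.

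**What to change.** Change the SAP as follows.

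1. Define the analysis row as a treatment course with its attempt number. Count all known earlier courses, including those given elsewhere or before 2016, and keep unknown history as its own category.
2. Report the all-lines rate by regimen as description only, and success by regimen separately for first-line and rescue courses.
3. Make the main regimen comparison within first-line courses, one course per patient.
4. As a supporting analysis, fit logistic regression to all courses with attempt number as a named covariate, using GEE or patient-clustered standard errors for repeated courses.

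The cost is SAP wording and one extraction check that attempt number is recorded per course and counts known outside courses.

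The loss of precision in the main comparison is small under the assumed 95% vs 70% mix. At n = 500 per regimen the 95% half-width goes from 1.96 × √[(0.7925 × 0.2075 + 0.755 × 0.245)/500] = 5.2 points to 1.96 × √[0.16/475 + 0.16/350] = 5.5 points. At 1,000 it goes from 3.7 to 3.9.

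Rescue-only comparisons will be imprecise: 1.96 × √[0.2275 × (1/25 + 1/150)] = 20 points at 500, and 14 at 1,000.

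Misrecorded history leaves some bias. If 20% of rescue courses are logged as first attempts, the first-line rates become (0.76 + 0.01 × 0.65)/0.96 = 79.8% and (0.56 + 0.06 × 0.65)/0.76 = 78.8%, a spurious gap of 1.0 point. At 50% the gap is 2.3 points.

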#### Multivariate Analysis

- Multivariable logistic regression to identify independent predictors of eradication success

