### 6.2 Secondary Outcomes

- Factors associated with eradication success or failure
- Comparison of eradication rates across regimens
- Distribution of comorbidities
- Number of eradication attempts before success

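### Regimen eradication rates are compared only without adjustment; the one adjusted analysis is a logistic model with no adjusted rates or rate differences planned

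*Combined protocol and SAP*

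**What the plan says.** The aims are expressed as rates. The primary objective (Section 2.1) is "To determine the real-world eradication success rate of different H. pylori eradication regimens". A secondary objective (Section 2.2) is "To compare the effectiveness of commonly used eradication regimens in routine clinical practice", and Section 6.2 lists "Comparison of eradication rates across regimens" as a secondary outcome.

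The study is not randomised. Section 3 states "All treatments are determined by treating physicians as part of routine care".

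Section 9.2 offers three layers of analysis that bear on this:

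- Descriptive: "Categorical variables: counts and percentages".
- Unadjusted: "Chi-square test for categorical variables".
- Adjusted: "Multivariable logistic regression to identify independent predictors of eradication success".

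Section 9.2 does not name an effect measure for the adjusted model, does not list its covariates, and does not say that regimen is one of them. It plans no adjusted rate, risk difference or risk ratio.

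The only information on the expected level of success is in Section 1: "eradication success rates remain suboptimal (<80% in internal data". This is an upper bound for the hospital overall. No rate is given for any regimen.

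**The concern.** When physicians choose the regimen, patients on different regimens may differ in ways that also affect eradication, such as earlier failed courses or comorbidity. The crude percentages and the chi-square test take no account of this. A reader will therefore look to the adjusted analysis for the regimen comparison.

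That analysis, reported in the usual way, answers on a different scale from the one the objectives use. An odds ratio does not say how many more patients per hundred are cured. Two regimens that differ by the same number of percentage points can have quite different odds ratios, and one odds ratio can stand for quite different gains. At stake is whether the report contains a confounding-adjusted answer to the study's own question about rates, or only a crude answer on the right scale and an adjusted one on another scale.

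**Working it through.** **Inputs.** The plan gives no figure of its own to reproduce on this point. Its estimate of about 3,000 patients (Section 9.1) is a count of eligible patients and does not enter the check. The only documented rate is the overall bound of below 80% (Section 1). All regimen rates below are assumptions. The 70% and 75% reference rates lie under that bound. The 80% row sits at the bound and is included to show the range.

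**Step 1: what one difference in rates looks like on each scale.** For a reference rate p0 and a comparison rate p1:

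- risk difference RD = p1 − p0
- rate ratio RR = p1 / p0
- odds ratio OR = [p1/(1 − p1)] / [p0/(1 − p0)]

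| p0 | p1 | RD | RR | OR |
|---|---|---|---|---|
| 0.70 | 0.80 | +10 points | 0.80/0.70 = 1.14 | 4.000/2.333 = 1.71 |
| 0.75 | 0.85 | +10 points | 0.85/0.75 = 1.13 | 5.667/3.000 = 1.89 |
| 0.80 | 0.90 | +10 points | 0.90/0.80 = 1.125 | 9.000/4.000 = 2.25 |

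The difference is the same in each row and the rate ratio hardly moves, but the odds ratio runs from 1.71 to 2.25. Read as a rate ratio, the 1.71 in the first row would imply 0.70 × 1.71 = 1.20, a success rate above 100%.

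**Step 2: what one odds ratio means at different reference rates.** Take OR = 1.5 and solve p1 = o/(1 + o), with o = 1.5 × p0/(1 − p0).

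| p0 | o | p1 | RD |
|---|---|---|---|
| 0.70 | 1.5 × 2.333 = 3.50 | 0.778 | +7.8 points |
| 0.80 | 1.5 × 4.000 = 6.00 | 0.857 | +5.7 points |
| 0.90 | 1.5 × 9.000 = 13.50 | 0.931 | +3.1 points |

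An odds ratio without a reference rate therefore does not give the difference in rates.

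**Step 3: whether the planned model can supply the missing quantity.** One simulation was run with 300,000 patients and assumed coefficients. A continuous covariate and an earlier-treatment indicator (25% of patients) affected both regimen choice and success; overall success was 75.8%. A logistic model with regimen and both covariates was fitted. Each patient's success was then predicted under each regimen in turn, and the predictions were averaged.

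- True standardised rates: 80.4% and 72.0%.
- Standardised rates from the fitted model: 80.3% and 72.0%; RD 8.3 points; RR 0.803/0.720 = 1.12.
- Crude rates in the same data: 79.9% and 72.4%, a difference of 7.5 points.
- Conditional odds ratio from the same fit: 1.64.

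So the planned model yields adjusted rates once the averaging step is added. This shows that the point estimates work when the model is correctly specified. It did not test the confidence intervals and says nothing about the size of confounding in the hospital's data.

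**The case against.** The strongest reply has four parts.

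1. A reader might infer that odds ratios exaggerate regimen differences. They do not: an odds ratio is a valid measure and misleads only if taken for a ratio of success rates. The plan never says it will be read that way, and never mentions the odds ratio. This stands, and the point does not rest on exaggeration.
2. A reader might also infer that the plan fails to deliver any comparison of rates. It does deliver one: percentages by regimen with a chi-square test. Section 6.2 does not say the comparison must be adjusted. This stands too. What is missing is the adjusted comparison on the rate scale, which matters because treatment was not randomised.
3. The logistic model's stated purpose is to find predictors, which fits the objective about factors linked to success or failure, and logistic regression is standard for that. This is correct, but no other adjusted analysis exists. Either this model also serves the regimen comparison, or that comparison has no adjustment at all.
4. The gap between odds ratio and rate ratio depends on which outcome is counted. For failure, 80% versus 90% success gives a risk ratio of 0.10/0.20 = 0.50 and an odds ratio of 1/2.25 = 0.44, which are much closer. This is right, but Section 6.1 and the logistic model both frame the outcome as success. Nor does modelling failure produce an adjusted rate or difference.

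Standardised rates are also only as credible as the covariates behind them. That is a reason to name the covariates, and it applies equally to the odds ratios.

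**Conclusion.** The point holds as a gap between the study's question and its planned output. The aims are on the rate scale and treatment was chosen by physicians, but no adjusted rate or difference in rates is planned. The logistic model and its tests remain valid.

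In size, a 10-point difference corresponds to a rate ratio of about 1.13 to 1.14 and an odds ratio of 1.71 to 1.89 for reference rates of 70% to 75%. An odds ratio of 1.5 can mean anything from 7.8 points at a 70% reference rate to 3.1 points at 90%.

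These figures rest on assumed regimen rates. It would be tempting to say that success is near 80%, but the documents give only an upper bound for the hospital as a whole. The conclusion needs only that success is common; the gap between the two ratios is already plain at 70% to 75%. It also assumes that the model would be reported by its usual output, since the plan names no other.

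**What to change.** Keep the logistic model and add to the Multivariate Analysis part of Section 9.2:

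- Regimen enters the model, together with a named list of patient and treatment-history covariates already collected under Section 5: for example age, sex, comorbidities, allergy history, other medication and how many courses had been tried before.
- The reported regimen comparison is the standardised (marginal) eradication rate for each regimen and the adjusted risk difference against a reference regimen stated in advance.
- Each has a 95% confidence interval by the delta method or bootstrap, clustered by patient if more than one course per patient is analysed.
- Odds ratios are shown as supporting output and are not described as ratios of rates.

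No new data are needed, and R is already among the named software. The cost is a revision of the SAP text and a little extra programming.
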